#### **6.2.5.1      Eliciting and Reporting Product Quality Complaints**

The investigator or designee must record all PQCs identified through any means from the receipt of the IMP from the sponsor or sponsor's designee, through and including reconciliation and up to destruction, including subject dosing. The investigator or

designee must notify the sponsor or sponsor's designee of the information indicated in [Section 6.2.5.2](#) by e-mail (address: [REDACTED]) immediately after becoming aware of any PQC.

Identification of a PQC by the subject should be reported to the site investigator, who should then follow the reporting mechanism above.

#### **6.2.5.2      Information Required for Reporting Product Quality Complaints**

- Description of complaint
- Reporter identification (eg, subject, investigator, site, etc.)
- Reporter contact information (eg, address, phone number, e-mail address)
- ID of material (product/compound name, kit number)
- Clinical protocol reference (number and/or trial name)
- Dosage form/strength (if known)
- Pictures of complaint sample (if available)
- Availability of complaint sample for return

#### **6.2.5.3      Return Process When Any Product Quality Complaint Is Received**

Indicate during the report of the PQC if the complaint sample is available for return. If the complaint sample is available for return, the sponsor will provide return instructions as needed.

It must be documented in the site accountability record that the complaint sample for a dispensed kit has been forwarded to the sponsor for complaint investigation.

#### **6.2.5.4      Assessment/Evaluation**

Assessment and evaluation of PQCs will be handled by the sponsor.

#### **6.2.6      Investigational Medicinal Product Reserve Sample Requirements**

Not applicable.

### **6.3      Measures to Minimize/Avoid Bias**

Since the primary endpoint in this trial is based on plasma drug concentrations, bias does not arise from not implementing blinding.

This trial will be conducted in a randomized, open-label, 2-arm, 2-period crossover fashion. Subjects who meet all of the inclusion criteria and do not fall under any of the exclusion criteria will be randomized at a 1:1 ratio to either the fasting-state-administration-first group or the fed-state-administration-first group on the day before

administration of the IMP in Period 1 (or on the day of IMP administration if preparation of the high-fat meal is completed in time).

## **6.4 Subject Compliance**

Subjects will be placed under the supervision of the investigator. The investigator will instruct subjects to:

- 1) Comply with the specified dose and regimen when taking the predosing product and IMP,
- 2) Adhere to the specified schedule during the trial,
- 3) Observe the lifestyle restrictions during the trial (see [Section 5.3](#)),
- 4) Cooperate in bowel-movement investigation from 3 days before IMP administration (Day -3) until 7 days postdose (Day 8) in Period 1 and Period 2,
- 5) Not take any prohibited concomitant medications (see [Section 6.5.1](#)),
- 6) Not receive any prohibited concomitant therapies (see [Section 6.5.1](#)), and
- 7) Not disclose any information obtained through participation in the trial to any third party.

For subjects who meet the criteria specified in [Section 7](#), the required measures must be taken.

## **6.5 Concomitant Medications or Therapies**

The investigator will record all medications (prescription medications, over-the-counter medications, herbal remedies, etc) and therapies taken by the subject from 30 days prior to signing of informed consent through the last scheduled contact in the source documents and eCRF. The investigator will record all medications and therapies taken by the subject for treatment of an AE or which caused an AE until the end of the trial (defined as the last date of contact or date of final contact attempt) in the source documents and eCRF.

For concomitant medications, the following will be recorded in the source documents and eCRF: medication, indication, dose, frequency, route, start date and end date. For concomitant therapy, the following will be recorded in the source documents and eCRF: therapy, indication, start date and end date.

### **6.5.1 Prohibited Concomitant Medications or Therapies**

The use of the following medications is prohibited from the specified date and time through the last scheduled contact:

The use of the following medications is prohibited from the specified date and time until completion of Day 14 examination in Period 2 or withdrawal examination:

[REDACTED]

[REDACTED]

[REDACTED]

[REDACTED]

[REDACTED]

[REDACTED]

The use of the following non-drug therapy is prohibited from the day of informed consent until completion of Day 14 examination or withdrawal examination in Period 2:

[REDACTED]

### **6.5.2      Restricted Concomitant Medications or Therapies**

The use of the following medications is restricted from the day of IMP administration in Period 1 until completion of Day 14 examination in Period 2 or withdrawal examination, except for prohibited concomitant medications:

- Antipsychotics other than brexpiprazole  
The use of other antipsychotics at a steady dose and regimen is permitted. The dose or frequency may be reduced at the discretion of the investigator in response to symptom improvement or maintenance or from a safety perspective. As-needed use is not allowed.  
The upper limit of dose and regimen of antipsychotics are as follows:
  - Antipsychotic medication comprising no more than 2 active components, and
  - A daily dose equivalent to  $\leq 600$  mg/day of chlorpromazine
    - If multiple antipsychotics are taken in the same day, this is to be the combined equivalent dose.
    - Chlorpromazine equivalent doses are based on Equivalent Conversion Table for Antipsychotics, as specified separately.

However, this does not include administration of antipsychotic medication at doses equivalent to less than 100 mg/day of chlorpromazine, which are not expected to have any antipsychotic effect.

- **Antiparkinsonian drugs and valbenazine**

The use of these medications is permitted only when extrapyramidal symptoms are present and such use is necessary in the opinion of the investigator. The dose and regimen must comply with the instructions in the package insert, and dosing within 12 hours before Drug Induced Extrapyramidal Symptoms Scale (DIEPSS) assessment must be avoided. Prophylactic use is not allowed. Therefore, in subjects who are using antiparkinsonian drugs or valbenazine at the time of informed consent, even if they are without a history of extrapyramidal symptoms related to the concomitant medications, use of these medications must be suspended by the day of IMP administration.

Before new use or dose increase of such medications, extrapyramidal symptoms will be assessed by DIEPSS.

- **Beta-blockers**

The use of  $\beta$ -blockers will be permitted only for the treatment of nonpsychiatric complications (eg, cardiovascular disorders) and only if the dose and regimen remain unchanged from before participation in the trial.

### **6.5.3      Rescue Medications**

Not applicable.

### **6.6      Intervention after the End of the Trial**

Not applicable.

## **7      Stopping Rules, Withdrawal Criteria, and Procedures**

### **7.1      Entire Trial or Treatment**

If the sponsor terminates or suspends the trial for any reason, prompt notification will be given to the head of the trial site and regulatory authorities in accordance with regulatory requirements.

### **7.2      Individual Site Discontinuation**

Individual trial site participation may be discontinued by the sponsor, the investigator, or the IRB/IEC/EC if judged to be necessary for medical, safety, regulatory, ethical, or other reasons consistent with applicable laws, regulations, and Good Clinical Practice (GCP).

The head of the trial site will notify the sponsor promptly if the investigator or the IRB/IEC/EC at the site discontinues participation in the trial.

## **7.3 Individual Subject Discontinuation**

### **7.3.1 Treatment Interruption**

Not applicable.

### **7.3.2 Treatment Discontinuation**

After treatment assignment, IMP administration may be discontinued for a variety of reasons. Treatment discontinuations may be initiated by a subject who is not satisfied with treatment or may become medically necessary due to AEs, required treatment with a disallowed medication or therapy, or other issues, as determined by the investigator. However, each investigator must comprehensively review the circumstances and offer the subject options for continued treatment to the degree possible as described in [Section 7.3.5](#).

### **7.3.3 Documenting Reasons for Treatment Interruption or Discontinuation**

A subject may discontinue the IMP for the reasons listed below. Only one reason for discontinuation (the main reason) and the date of discontinuation will be recorded in the source documents and eCRF. Any AE related to treatment discontinuation must always be regarded as the reason for the discontinuation.

- Adverse event
  - Death
  - Continuing IMP places the subject at undue risk as determined by the investigator
    - Safety concern that is possibly, probably, or likely related to IMP
    - SAE
    - Exacerbation or progression of the underlying disease
  - Subject decides to discontinue because of annoyance or discomfort due to a nonserious AE which is not otherwise determined to be an undue hazard
  - Subject vomits within 12 hours after IMP administration
  - Subject shows allergic reaction or hypersensitivity to brexpiprazole
  - Other potentially IMP-related safety concerns or AEs
- Occurrence of major protocol deviation
  - Failure to meet the inclusion/exclusion criteria (however, treatment discontinuation based on assessment of the results of clinical laboratory tests and central ECG assessment in Period 1 baseline examination is not considered a protocol deviation)
  - Randomized by mistake

- Subject uses, or it is considered that the subject needs to use, any prohibited concomitant medication or therapy
- Noncompliance with IMP administration
  - Failure to take the specified number of IMP tablets on the day of IMP administration
- Protocol-specific withdrawal criterion met
  - Prior to IMP administration in Period 1 and Period 2, the subject is unable to finish the prescribed high-fat meal within 30 minutes after starting to eat and also fails to complete IMP administration after finishing eating within 30 minutes after starting to eat (however, the date of IMP administration may be postponed once only, after consultation with the subject)
  - Subjects with a positive drug screen for cocaine, or subjects with a positive drug screen for any other drug who are dependent on the drug or are unlikely to overcome their drug dependency in the opinion of the investigator
  - Subjects with a positive alcohol breath test who are dependent on alcohol or are unlikely to overcome their alcohol dependency in the opinion of the investigator
- Lost to follow-up
- Investigator's decision (other than AE)
- Pregnancy (see [Section 10.3](#))
- Trial site terminated by sponsor
- Trial terminated by sponsor
- Request by the subject's parent/legal guardian to discontinue treatment (including consent withdrawal by the subject's parent/legal guardian)
- Request by the subject to discontinue treatment (including consent withdrawal by the subject)
- Other

If the subject discontinues IMP due to an AE, the investigator, or other trial personnel, will make every effort to follow the event until it has resolved or stabilized. Follow-up procedures in [Section 7.3.2](#) must be followed.

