## 4 Trial Design

### 4.1 Type/Design of Trial

The trial design schematic is shown in [Figure 1.2-1](#) and the schedule of assessments is shown in [Table 1.3-1](#).

This is a multicenter, randomized, open-label, 2-arm, 2-period crossover trial to investigate the effects of food on the PK of brexpiprazole QW formulation in patients with a diagnosis of schizophrenia (295.90) based on DSM-5®. The trial consists of 2 periods, namely, the screening period and the IMP administration period (including washout period and follow-up period). The IMP administration period comprises Period 1 and Period 2 to investigate the effects of food on the PK of brexpiprazole QW formulation 48 mg, in which a single oral dose of brexpiprazole QW formulation will be administered at 48 mg in a fasting state or within 10 minutes of finishing a high-fat meal employing a 2-arm, 2-period crossover design. The sample size necessary for the trial assessment is a total of 36 subjects as trial completers.

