### **6.1.2      Investigational Medicinal Product**

The IMP administration method is indicated below. Please refer to [Section 4.1](#) for the administration method and treatment duration for each period and each treatment group. Regarding the status of trial treatment, the date and time of IMP administration and the dose (the number of tablets taken) will be recorded in the source documents and eCRF. The status of meal consumption will also be recorded in the source documents and eCRF (see [Section 5.3.1](#)).

- 1) IMP: brexpiprazole QW formulation 24 mg tablet
- 2) Dose and regimen

#### Period 1 and Period 2

Subjects who meet all of the inclusion criteria and do not fall under any of the exclusion criteria will be randomized at a 1:1 ratio to either the fasting-state-administration-first group or the fed-state-administration-first group on the day before administration of the IMP in Period 1 (or on the day of IMP administration if preparation of the high-fat meal is completed in time) and will receive the IMP in Period 1 and Period 2 as follows. To the extent possible, the IMP will be administered at approximately the same time of day in both Period 1 and Period 2. [REDACTED]

[REDACTED]  
[REDACTED]  
[REDACTED] For administration in the fed state in Period 1 or Period 2, if the high-fat meal cannot be eaten completely during the period specified in [Section 5.3.1](#), the date of IMP administration may be postponed once only, after consultation with the subject.

- 1) Fasting-state-administration-first group

In Period 1, a single oral dose of two 24 mg tablets of brexpiprazole QW formulation (48 mg as brexpiprazole) will be administered with approximately

150 mL of water following at least 10 hours of fasting. In Period 2, following at least 10 hours of fasting, the subject will consume a high-fat meal within 20 minutes, after which a single oral dose of two 24 mg tablets of brexpiprazole QW formulation (48 mg as brexpiprazole) will be administered with approximately 150 mL of water within 10 minutes of finishing the meal.

2) Fed-state-administration-first group

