In Period 1, following at least 10 hours of fasting, the subject will consume a high-fat meal within 20 minutes, after which a single oral dose of two 24 mg tablets of brexpiprazole QW formulation (48 mg as brexpiprazole) will be administered with approximately 150 mL of water within 10 minutes of finishing the meal. In Period 2, a single oral dose of two 24 mg tablets of brexpiprazole QW formulation (48 mg as brexpiprazole) will be administered with approximately 150 mL of water following at least 10 hours of fasting.

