### 3.2 Trial Treatments

A single oral dose of two 24 mg tablets of brexpiprazole QW formulation (48 mg as brexpiprazole) will be administered with approximately 150 mL of water in a fasting state (following at least 10 hours of fasting) or within 10 minutes after the completion of a high-fat meal consumed over 20 minutes or less following at least 10 hours of fasting.

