## 5 Statistical Analysis Sets

## 5.1 Food Effect Analysis Set

The food effect analysis set includes all subjects for whom  $C_{max}$ ,  $AUC_{\infty}$  or  $AUC_t$  could be calculated throughout Period 1 and Period 2.

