## 10.3 Technical Details for Pharmacokinetic Statistical Analysis

### 1) Exclusion of Data

The following data will be rejected and excluded from pharmacokinetic analyses:

- [REDACTED]
- Plasma drug concentrations after use of prohibited concomitant medications or foods that may affect the PK of brexpiprazole, and pharmacokinetic parameters calculated using rejected concentrations
- Plasma drug concentrations after failure to receive the IMP according to the conditions specified in the protocol (Section 5.3.1 and Section 6.1.2), and pharmacokinetic parameters calculated using rejected concentrations
- Plasma drug concentrations in samples collected outside the protocol-specified acceptable window (Table 1.3-2) of blood sampling time points. These data will be excluded from the calculation of descriptive statistics of concentrations at the time points, but will be used for the calculation of pharmacokinetic parameters.
- Plasma drug concentrations and pharmacokinetic parameters in a period for compounds for which the predose plasma drug concentrations exceed 5% of  $C_{max}$  during that period
- Plasma drug concentrations or pharmacokinetic parameters judged to be inappropriate by the clinical pharmacologist for other reasons than the above. In this case, the reason for judging them to be inappropriate will be recorded.

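### Do the differing meal and dosing time limits (20 + 10 minutes against 30 minutes) leave completers without a usable fed-period result?

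*Protocol*

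**What the plan says.** - **Dosing instruction.** In Protocol 6.1.2, for fed administration, "the subject will consume a high-fat meal within 20 minutes", and the tablets follow "within 10 minutes of finishing the meal". The synopsis, Protocol 4.3.1 and SAP 3.2 agree; SAP 3.2 has dosing "within 10 minutes after the completion of a high-fat meal consumed over 20 minutes or less following at least 10 hours of fasting". Inclusion criterion 7 also uses 20 minutes.
- **Postponement.** Under Protocol 6.1.2 the dosing date may be moved once "if the high-fat meal cannot be eaten completely during the period specified in" Section 5.3.1. The text of 5.3.1 is redacted.
- **Withdrawal reason.** Protocol 7.3.3 lists, among the reasons for which a subject may discontinue, being "unable to finish the prescribed high-fat meal within 30 minutes after starting to eat and also fails to complete IMP administration after finishing eating", with the dosing part also counted to 30 minutes from the start of eating. It too allows one postponement.
- **Data rejection.** SAP 10.3 rejects "Plasma drug concentrations after failure to receive the IMP according to the conditions specified in the protocol (Section 5.3.1 and Section 6.1.2"), together with the parameters derived from those concentrations.
- **Analysis set.** SAP 5.1 takes subjects whose Cmax or AUC "could be calculated throughout Period 1 and Period 2". SAP 5.3 rules out imputation.
- **Sample size.** Protocol 4.1 states: "The sample size necessary for the trial assessment is a total of 36 subjects as trial completers". Protocol 4.5 defines a completer by the Day 14 blood sample of Period 2.

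**The concern.** Three decisions hang on meal and dose timing: whether to postpone or withdraw, whether to count the subject as a completer, and whether to use the fed-period data. As printed they need not agree. Protocol 7.3.3 has no separate limits for the meal and for the gap to dosing. Its *and also* makes the dosing part idle: a meal unfinished at 30 minutes already rules out dosing after it by 30 minutes, so a late dose alone never meets the criterion.

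A subject could thus be dosed outside 6.1.2, stay in the trial, give the Day 14 sample and count towards the 36, and then have the fed-period Cmax and AUC rejected. Such losses would arise only in the fed condition. The synopsis aims for a 90% interval inside 0.8–1.25, and that depends on subjects with usable parameters in both periods, not on completers. The fear is that 36 completers deliver less precision than planned.

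**Working it through.** **1. The two timing rules side by side** (minutes from the start of eating)

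| Meal ends / dose | Breaks 6.1.2? | Meets 7.3.3, both parts required | Meets 7.3.3 if either part suffices |
|---|---|---|---|
| 20 / 30 | no | no | no |
| 25 / 29 | yes (meal) | no | no |
| 28 / 35 | yes (meal) | no | yes |
| 19 / 35 | yes (16 min to dose) | no | yes |
| 31 / 36 | yes (meal) | yes | yes |

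The outer limits coincide: 20 + 10 = 30. If 7.3.3 is taken to mean that meal and dose must both be complete by minute 30, the gap shrinks to subjects who exceed a component limit but are dosed by then (row 2).

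**2. What happens to such a subject**

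- Protocol 6.1.2 requires the dose time and the meal status to be recorded. The SAP lists meals (PDATA-17), dosing (SMED-1) and exclusions from analysis sets (SUBEX-1).
- Protocol 10.1.5 sends significant deviations, dosing errors included, to a joint decision of investigator and sponsor on continuation. SAP 7.5 tabulates major deviations in IMP administration and in procedures that affect the primary endpoint.
- SAP 10.3 then rejects the fed-period data. This rule turns on how the dose was taken, not on the concentrations found.

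**3. Cost in precision**

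The plan's 36 cannot be reproduced, because the within-subject CV and target power are redacted. The CV and the losses below are assumptions.

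Inputs: true ratio 1, limits 0.8–1.25, two-sided 90% interval, 1:1 allocation. Formulas: σ² = ln(1 + CV²); SE = σ√(2/N); df = N − 2; half-width = t(0.95, df) × SE. Power is the expectation over the residual SD s of 2Φ[(ln 1.25 − t·s·√(2/N)) / (σ√(2/N))] − 1, taken as zero where the bracket is negative.

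Interval at CV 30%: σ = √ln 1.09 = 0.2936.

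- N = 36: SE = 0.2936 × √(2/36) = 0.0692; half-width = 1.691 × 0.0692 = 0.117; interval 0.890–1.124.
- N = 34: SE = 0.2936 × √(2/34) = 0.0712; half-width = 1.694 × 0.0712 = 0.121; interval 0.886–1.128, about 3.1% wider on the log scale.

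| Assumed CV | N = 36 | N = 34 | N = 30 |
|---|---|---|---|
| 20% | 0.998 | 0.996 | 0.991 |
| 25% | 0.966 | 0.956 | 0.925 |
| 30% | 0.870 | 0.845 | 0.780 |
| 35% | 0.722 | 0.684 | 0.596 |

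Losing two subjects costs about 0.1, 1.0, 2.5 and 3.8 points in turn. With 36 evaluable, power is 80% at a CV of about 32.5% and 90% at about 28.8%. The last row would therefore apply only if 36 had been chosen with less than 80% power.

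**4. Does it matter whether a rejected parameter counts as calculated under SAP 5.1?**

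If two of 36 lose the fed period and are dropped, the variance of the food effect rises by 36/34 = 1.059. If they stay in the mixed model with the fasting period only, it rises by 1.044 to 1.056 (assumed within-subject correlation 0.5 to 0.9). For four of 36 the figures are 36/32 = 1.125 against 1.094 to 1.119. The choice hardly moves the result.

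**The case for a change.** The strongest case for a change is that redaction does not fully excuse the mismatch. If 5.3.1 says 20 minutes, its postponement trigger differs from that in 7.3.3. If it says 30, it differs from 6.1.2, and SAP 10.3 cites both sections. Only an explicit tolerance would bring them into line. Completion is defined by a blood draw, so completers and evaluable subjects can differ by other routes as well, such as a predose concentration above 5% of Cmax or a prohibited medication. Settling the rule beforehand would also spare case-by-case exclusions in an open-label trial.

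Part of this stands. The *and also* wording is faulty, the component limits do not match, and the visible text does not say whether 36 allows for non-evaluable completers. It does not carry further, for three reasons. No passage tells sites to dose outside 6.1.2, and a reason for which a subject may discontinue can be wider than a dosing instruction without contradicting it. The completer count is a general point that meal timing does not create, and the redacted sample-size sections may already hold an allowance. Finally, six losses have no support in the documents: subjects must be able to finish the meal in 20 minutes, dosing is inpatient, and one postponement is available.

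**Conclusion.** No change to the analysis follows. Followed as written, the plan rejects fed data obtained outside the stated conditions, and the fed/fasting interval remains valid for the conditions the protocol describes. The loss is in precision only: about 0.1 to 2.5 points of power for two lost subjects at a CV of 20–30%, and an interval at CV 30% of 0.886–1.128 instead of 0.890–1.124.

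This rests on an assumed CV, on few affected subjects (the documents give no frequency), and on slow eating not being linked to a different food effect. A loss of six would cost about 9 points at CV 30%, but nothing in the documents points to that number.

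What remains is clerical. The timing statements in Protocol 5.3.1, 6.1.2 and 7.3.3 and the rejection rule in SAP 10.3 must be reconciled by the sponsor, who decides the limits; no view is taken here on which is right. That alters no stated figure and no planned analysis.
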